9.0 Follow-up and Record Retention

In total, this study will last five years (2017-2022), with patients remaining in follow-up for two years within that time frame. Patient information and research results will be deidentified to maintain participants' privacy. Clinical records with identifiable information will be destroyed at the conclusion of the study. De-identified information used for analysis purposes (those described here and potential subsequent analyses with deidentified information) may be retained for an indefinite period of time following conclusion of the study.

10.0 Foreign Justification

To be able to successfully answer the scientific questions posed by this study, the study setting must be one that has a high prevalence of three things: HIV, chronic kidney disease, and *APOL1* risk alleles. As aforementioned, Nigeria has a significant HIV/AIDS burden, and while the prevalence of CKD in HIV positive ART-naive patients varies from 6 to 48% across sub-Saharan Africa, the highest prevalence has been reported in Nigeria. The frequency of *APOL1* risk alleles is also highest in West Africa, specifically in Nigeria among persons of Yoruba and Igbo descent. Furthermore, the study team has long-established collaborations in Nigeria, including the completion of NIH-funded clinical research studies (including an RCT). Therefore, Nigeria provides the optimal setting to conduct this study.

ACTIVITIES		MONTHS								
	0-6	6-12	12-18	18-24	24-30	30-36	36-42	42-48	48-54	54-60
Introductory meeting										
Protocol development, including MOPs, CRFs										
IRB approvals										
DSMB review										
Hire and train study staff										
Pilot test surveys/forms, study kick-off										
Participant screening/enrollment-Aim 1										
Genotyping (APOL1 SNPs) Aim 1										
Participant enrollment/randomization- Aim 2										
Follow-up visits with lab assessments- Aim 2										
Data collection										
Data management and QC										
Data analysis										
Dissemination of study findings, manuscript writing										

Appendix A. Study Timeline

LEGEND: MOP = manual of operations, CRF = Case review forms, QC = quality control

Appendix B. Supplemental tables - Statistical calculations for secondary endpoints

Table S1. Detectable differences in means of log-transformed uACR values. The outcome is uACR measurement (units= mg/g) and a t-test will be used to compare the two means of log-transformed uACR for the two arms after follow-up. Given the inclusion criteria with the uACR range of 30-300 mg/g, we assume the log-transformed uACR has

a 95% probability interval from 3.4 to 5.7 and a standard deviation of 0.58. With 90 subjects at the end of study after adjustment for 10% loss to follow up (LTFU), we will have 80% power to detect a difference of 0.42 units of standard deviation (0.24 on log-transformed means assuming standard deviation of 0.58).

,		
alpha	Subjects per	Detectable
	Arm	Difference
0.010	100	0.30
0.010	120	0.27
0.010	140	0.25
0.010	160	0.23
0.010	180	0.22
0.017	100	0.28
0.017	120	0.25
0.017	140	0.24
0.017	160	0.22
0.017	180	0.21
0.025	100	0.27
0.025	120	0.24
0.025	140	0.23
0.025	160	0.21
0.025	180	0.20
0.050	100	0.24
0.050	120	0.22
0.050	140	0.20
0.050	160	0.19
0.050	180	0.18

Table S2. Detectable differences in doubling of serum creatinine. Assuming 2% - 20% of subjects in the SOC arm will be doubling of serum creatinine, we will use an uncorrected chi-squared test to detect the difference between the two arms. In case of 10% of subjects on the SOC arm will have their serum creatinine doubled after follow up, we will have 80% power to detect a 9.3% decrease on the experimental arm to 0.7% (RR=0.07).

Alpha	Rate SOC	Detectable	Rate Exp
	arm	RR	arm
0.01	0.10	0.050	0.005
0.01	0.15	0.193	0.029
0.01	0.20	0.290	0.058
0.05	0.10	0.180	0.018
0.05	0.15	0.307	0.046
0.05	0.20	0.395	0.079

Table S3. All-cause mortality. With 140 patients on each arm, we will have 126 patients on each arm at the end of study assuming 10% LTFU. An uncorrected chi-square test will be used to test the difference of the all-cause mortality between the two arms. In case of the all-cause mortality is 10% on the SOC arm, we will have 80% power to detect an absolute 8.2% decrease on the treatment arm to 1.8%.

Rate of SOC	Power	Detectable Difference	RR	Detectable Rate Exp Arm
0.08	0.8	0.072	0.10	0.008
0.08	0.9	0.079	0.01	0.001
0.10	0.8	0.082	0.18	0.018
0.10	0.9	0.091	0.09	0.009
0.12	0.8	0.092	0.23	0.028
0.12	0.9	0.102	0.15	0.018
0.14	0.8	0.100	0.29	0.040
0.14	0.9	0.112	0.20	0.028
0.16	0.8	0.108	0.32	0.052
0.16	0.9	0.121	0.24	0.039
0.18	0.8	0.115	0.36	0.065
0.18	0.9	0.129	0.28	0.051
0.20	0.8	0.121	0.39	0.079
0.20	0.9	0.136	0.32	0.064

Table S4. Decline in eGFR. Proportion experiencing a 40% decline in eGFR (using CKD-EPI-Cr-CyC equation). With 140 patients per arm, assuming 10% LTFU, in case of 50% patients experienced a 40% decline in eGFR on the SOC arm, we will have 80% power to detect a relative 34% decrease on the treatment arm to 33% with 5% type I error.

Power	Rate SOC	RR	Rate Exp
	arm		Arm
0.8	0.20	0.40	0.08
0.9	0.20	0.32	0.06
0.8	0.25	0.46	0.12
0.9	0.25	0.39	0.10
0.8	0.30	0.51	0.15
0.9	0.30	0.45	0.13
0.8	0.35	0.56	0.20
0.9	0.35	0.50	0.17
0.8	0.40	0.59	0.24
0.9	0.40	0.54	0.22
0.8	0.45	0.63	0.28
0.9	0.45	0.57	0.26
0.8	0.50	0.66	0.33
0.9	0.50	0.61	0.30
0.8	0.55	0.68	0.38
0.9	0.55	0.64	0.35
0.8	0.60	0.71	0.43
0.9	0.60	0.66	0.40

Table S5. Mean change in eGFR. Mean change in eGFR over time (using CKD-EPI-Cr-Cyc equation) with 126 patients per arm after LTFU. Detectable difference shown as unit of 1 SD.

Power	Detectable Difference
0.8 0.9	0.35 0.41

Table S6. Change in quality of life (QOL) score. The change in clinical/performance status (as ascertained via two measures, specifically the WHO guality of life (WHOQOL-HIV) tool (31 questions) and the Karnofsky performance score. WHOQOL-HIV evaluates quality of life based on six domains (physical, psychological, level of independence, social relationships, environment, and spiritual/beliefs) and includes questions specific to HIV/AIDS. The brief version contains 31 questions and each question is rated on a 5point Likert scale. For the analysis of the data, the scores of the questions within each domain are averaged to get the domain score. The final score will be the mean of domain scores multiplied by 4. The final score has a minimum value of 4 and maximum value of 20. Hence, we assume it has a standard deviation of 4. With 126 subjects on each arm after LTFU, we will have 80% power to detect a 1.4 points difference in means of WHOQOL-HIV scores, and 90% power to detect a 1.6 points difference in the overall WHOQOL-HIV scores between two arms. The Karnofsky Performance Score has a range of values from 100 to 0, where 100 is "perfect" health and 0 is death. We assume it has standard deviation of 25. With 126 subjects on each arm after LTFU, we will have 80% power to detect an 8.7-point difference in means of Karnofsky Performance Score, and 90% power to detect a 10-point difference in the means of Karnofsky Performance Score between two arms.

Power	Detectable Difference
0.8 0.9	0.35 0.41

Table S7. Change in TDF toxicity. Conservatively, we estimate 2% of patients will experience grade 3 or higher TDF toxicities. In this study, renal events are defined as i) a rise in serum creatinine to > 1.9 and ii) a drop in eGFR to < 50 ml/min. Given 126 patients on each arm after LTFU, assuming 2% TDF toxicity on the SOC arm, we will have 31% power to detect a relative 95% decrease from 2% to 0.1% with 5% type I error, or we have 83% power to detect an increase of toxicity from 2% on the SOC arm to 11% on the treatment arm.

Power	Detectable Difference	RR	Detectable Rate Exp Arm
0.07	0.01	1.5	0.03
0.15	0.02	2.0	0.04
0.25	0.03	2.5	0.05
0.37	0.04	3.0	0.06
0.48	0.05	3.5	0.07
0.59	0.06	4.0	0.08
0.69	0.07	4.5	0.09
0.77	0.08	5.0	0.10

0.83	0.09	5.5	0.11
0.88	0.10	6.0	0.12

Table S8. Change in blood pressure (BP). Recent research (Sakajiki, et al. Kidney disease in HIV/AIDS patients, Annals of Nigerian Medicine. Jul-Dec 2014. Vol 8. Issue 2) indicates SBP or DBP with standard deviation from 13.81 to 20.18 mmHg. We conservatively assume that BP will have a SD of 20 mmHg. With 126 subjects on each arm after LTFU, we will have 80% power to detect a 7-mmHg difference in means of BP, and 90% power to detect an 8.2 mmHg difference in the means of BP between two arms with 5% type I error.

Power	Detectable Difference
0.8	0.35
0.9	0.41

BIBLIOGRAPHY

- 2. Palella FJ, Jr., Baker RK, Moorman AC, et al. Mortality in the highly active antiretroviral therapy era: changing causes of death and disease in the HIV outpatient study. *Journal of acquired immune deficiency syndromes (1999)*. 2006;43(1):27-34.
- 3. The Antiretroviral Therapy Cohort C. Causes of Death in HIV-1–Infected Patients Treated with Antiretroviral Therapy, 1996–2006: Collaborative Analysis of 13 HIV Cohort Studies. *Clinical infectious diseases : an official publication of the Infectious Diseases Society of America.* 2010;50(10):1387-1396.

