- Significantly higher proportions of participants in the SOC arm (60% vs. 25% in the intervention arm) will progress from microalbuminuria to macroalbuminuria (uACR>300 mg/g).
- Albuminuria will fall by an average of 40% in the intervention arm and increase by an average of 10% in the SOC arm.

Study population: All HIV-positive ART-experienced (6+ months) screened individuals (n = 2,600) found to have i) confirmed microalbuminuria (mean uACR between 30-300 mg/d obtained at 2 separate measurements at least 4 and no more than 8 weeks apart), (NOTE: based on variability of individual uACR measurements, we also plan to call back Aim 1 participants having normoalbuminuria (especially those with an average uACR value in the 20-29 mg/g range) as well as Aim 1 participants having macroalbuminuria), and ii) fairly well-preserved renal function, namely an eGFR > 60 ml/min/1.73m²; will be approached for enrollment into this study. Based on recent studies at AKTH among HIV positive adults, we anticipate that a minimum of 18% of screened patients (n~460) will be eligible. Therefore, with a target sample size equal to

280 (see Section 10.0), 59% of eligible patients would need to consent for this Aim 2 study.

Primary Endpoints:

- i) Regression from microalbuminuria (uACR=30-300 mg/g) to normoalbuminuria (uACR < 30 mg/g)
- ii) Progression from microalbuminuria (uACR=30-300 mg/g) to macroalbuminuria (uACR > 300 mg/g) by study arm
- iii) Mean change in uACR

Secondary Endpoints:

i) Doubling of serum creatinine from baseline; ii) All-cause mortality (**NOTE**: Planned follow-up is two years for all participants), iii) Proportion experiencing a 40% decline in eGFR (using CKD-EPI-Cr-CyC equation), iv) Mean change in eGFR over time (using CKD-EPI-Cr-CyC equation), and v) change in clinical/performance status (as ascertained via two measures, specifically the WHO quality of life (WHOQOL-HIV) tool (31 questions)^{107,108} and the Karnofsky performance score)¹⁰⁹.

1.3 Specific Aim 3

Specific Aim 3: To determine whether the *APOL1* HR genotype is associated with worse longitudinal kidney outcomes among HIV-positive Nigerians with prevalent albuminuria, with regard to progression of albuminuria and eGFR decline.

Hypothesis: After two years of follow-up, independent of baseline uACR, eGFR, and/or treatment assignment:

- Study participants with the HR genotype will have a more rapid kidney function decline (median eGFR change) compared to those with the LR genotype.

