enroll 280 eligible patients from Specific Aim 1 for 1:1 randomization in our RCT for Specific Aim 2. Based on our prior experience with ongoing RCTs in the study location, we anticipate that enrollment into Aim 2 will take 12 months and there will be 10% loss to follow up at end of year 2, yielding 252 patients on study (126 per arm). Aim 2A: At 2 years, we hypothesize that a higher proportion of intervention participants will regress from microalbuminuria to normoalbuminuria (uACR < 30 mg/g) with a hazard ratio (HR)= 2.50. Using the logrank test, we will have approximately 80% power if the rate of regression in the SOC arm is at least 12%, and 90% power if that rate is 16% or higher with a 1.7% type I error¹³⁶. (The type I error rate was set at 5%/3=1.7% to account for multiple testing and the fact that we have 3 primary endpoints.) See Tables 3 and 4. Aim 2B: At 2 years, we hypothesize that a higher proportion of patients in the SOC arm. namely 60% vs. 25% in the intervention arm (HR≈0.42), will progress from microalbuminuria to macroalbuminuria (uACR > 300 mg/g). With 126 patients per arm (after removing 10% loss to follow-up), we will have >95% power for Aim 2B with a 1.7% type I error. See Tables 5 and 6. Figure 3 shows changes in Aim 2A power for varying SOC regression rates and changes in Aim 2B power for varying sample size. The sample size for Aim 2C is such that we will have approximately 80% power to detect at the alpha=0.017 level a difference in the log-transformed mean uACR of 0.24, which is approximately 0.41 standard deviations. These power calculations are likely conservative, as they do not incorporate baseline covariates, which will be included in the actual analyses (see below) and should improve power; in addition, the uACR analysis will incorporate multiple longitudinal measures per person whereas these power calculations only assume a single final measurement per person.

The sample size was chosen to have sufficient power for all primary endpoints. Tables S1-S8, investigating power and detectable alternatives for the secondary endpoints with a total sample size of 280 are provided in Appendix B. In short, we anticipate low power to detect differences between intervention arms in the doubling of serum creatinine, all-

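### The Aim 2C power rests on an SD of 0.58 taken from the eligibility window, which the plan's own follow-up rates do not support

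*Combined protocol and SAP*

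**What the plan says.** Mean change in uACR is the third primary endpoint of Aim 2. Its power basis is Table S1 in Appendix B, which sits under a heading for secondary endpoints. The text there starts from the uACR limits for entry and gives the log values "a 95% probability interval from 3.4 to 5.7 and a standard deviation of 0.58". The same paragraph names the test: "a t-test will be used to compare the two means of log-transformed uACR for the two arms after follow-up".

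The sample size justification for Specific Aim 2 in Section 8.0 claims "approximately 80% power to detect at the alpha=0.017 level" for "a difference in the log-transformed mean uACR of 0.24, which is approximately 0.41 standard deviations". The level comes from splitting 5% over three endpoints: "The type I error rate was set at 5%/3=1.7% to account for multiple testing". The section expects 126 patients per arm after 10% loss. It describes the power calculations as probably conservative, because they leave out baseline covariates and repeated measurements.

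The other two primary endpoints carry their own assumptions. For progression, Section 1.2 says "Significantly higher proportions of participants in the SOC arm (60% vs. 25% in the intervention arm) will progress from microalbuminuria to macroalbuminuria". For regression below 30 mg/g, Section 8.0 uses a SOC rate of at least 12% with a hazard ratio of 2.5, and its power table for regression pairs 12% with 30% in the intervention arm (16% with 40%). For mean uACR, Section 1.2 says "Albuminuria will fall by an average of 40% in the intervention arm and increase by an average of 10% in the SOC arm". No SD of uACR at follow-up appears anywhere in the document.

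**The concern.** An SD read off the entry window describes patients selected to lie in 30-300 mg/g. Nothing holds them there for two years, and two of the three primary endpoints count patients who leave. An SD of 0.58 centred on the window puts about 5% of values outside it. The plan's rates put 72% (60% + 12%) of the SOC arm and 55% (25% + 30%) of the intervention arm outside, if read as status at two years. If the real spread is wider, the unadjusted test has less power for 0.24 than stated.

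The assumptions behind endpoints ii and iii also pull against each other: a SOC arm whose average uACR rises by only 10% is not an obvious source of 60% progression to above 300 mg/g. At stake is whether the stated power for Aim 2C, and the event rate behind the stated Aim 2B power of more than 95%, have a basis.

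**Working it through.** **1. Origin of the SD.** ln 30 = 3.40 and ln 300 = 5.70. (5.7 - 3.4)/4 = 0.575 and (5.7 - 3.4)/3.92 = 0.587. So 0.58 is the window expressed as an SD.

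**2. The plan's figure.** n = 126 per arm, alpha 0.017. Sidedness is not stated; two-sided reproduces the figure.
- Detectable difference at 80% power = (2.387 + 0.842) x 0.58 x sqrt(2/126) = 0.236, or 0.407 SD.
- Power for 0.24 = Phi(0.24/(0.58 x 0.126) - 2.387) = 0.815 (0.810 with the noncentral t).

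Both agree with Section 8.0. (The 90 subjects and 0.42 SD in the Table S1 text instead match 90 per arm at alpha 0.05.)

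**3. Smallest SD compatible with the rates, if they are status at two years.** Let p be the share above ln 300 and q the share below ln 30. Variance is smallest when progressors sit exactly at ln 300, regressors exactly at ln 30, and everyone else at the mean. This gives SD = ln(10) x sqrt(pq/(p + q)), with no normality assumption.
- SOC, p = 0.60, q = 0.12: 2.303 x sqrt(0.072/0.72) = 0.73.
- Intervention, p = 0.25, q = 0.30: 2.303 x sqrt(0.075/0.55) = 0.85.
- Pooled: sqrt((0.73² + 0.85²)/2) = 0.79.

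**4. Power by SD** (126 per arm, alpha 0.017, normal formula). The hypothesised effect, read as a ratio of geometric means, is ln(1.10/0.60) = 0.606.

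| SD | Detectable difference, 80% power | Power for 0.24 | Power for 0.606 |
|---|---|---|---|
| 0.40 | 0.16 | 0.99 | >0.99 |
| 0.58 | 0.24 | 0.82 | >0.99 |
| 0.79 | 0.32 | 0.51 | >0.99 |
| 1.00 | 0.41 | 0.31 | 0.99 |
| 1.30 | 0.53 | 0.18 | 0.91 |
| 1.50 | 0.61 | 0.13 | 0.79 |

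The SD at which 0.606 has exactly 80% power is 0.606/(3.229 x 0.126) = 1.49.

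**5. Effect of baseline adjustment.** Residual SD = SD x sqrt(1 - r²). With an assumed correlation r = 0.7, 0.79 becomes 0.56 and 1.0 becomes 0.71. The documents give no r.

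**6. If the rates are cumulative first crossings.** The bounds in step 3 then do not strictly apply, so I simulated eight 3-monthly SOC visits with a 10% geometric-mean rise over two years. All other inputs are assumptions: baseline log-uniform on 30-300, or half in 30-59 and half in 60-300 as the strata in Section 5.0 plan; visit noise SD 0.3-0.7; between-patient two-year drift SD 0-1.0, on the log scale. Results:
- SD at the last visit: about 0.7 to 1.4.
- Residual SD given baseline: about 0.3 to 1.2.
- Ever above 300 mg/g: about 15% to 49%. No scenario reached 60%.

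**7. Aim 2B.** The plan's 60% and 25% give 126 x 0.85 = 107 events. Power = Phi(|ln 0.42| x sqrt(107)/2 - 2.387) = 0.98, as its progression table shows. With proportional hazards (intervention rate = 1 - (1 - SOC rate)^0.42), a cumulative SOC rate of 49% gives 93 events and power 0.96. A rate of 30% gives 55 events and power 0.80.

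**The case against.** The strongest reply is that the Table S1 t-test is not the planned analysis. Section 8.0 specifies a linear mixed model on 3-monthly uACR, adjusted for baseline uACR, and says that the power calculation leaves this gain out. The SD that matters is then the residual SD, and 0.58 lies inside the simulated range of 0.3 to 1.2. This stands: the text does not show that Aim 2C has less than 80% power for 0.24. It does not make 0.58 a justified value, since the window says nothing about residual spread after two years.

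It is also fair that the progression and regression rates feed log-rank and Cox analyses. Section 8.0 words both as proportions at two years, but if they count first crossings at any visit, fewer patients are outside the window at a given visit and one patient may count in both directions. That is why the bounds of 0.73 and 0.85 are conditional.

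Four stronger readings are tempting but not supported:
- A reader might fit a log-normal to the stated tails and infer an SD several times 0.58. That needs log-normality as well as two-year status, and implies upper percentiles of tens of thousands of mg/g.
- A reader might infer that the assumptions for endpoints ii and iii cannot both be true, so that one stated power must be wrong. A 10% average rise coexists with up to 49% ever crossing in the simulations; 60% looks optimistic, but impossibility is not shown.
- A reader might put the share above 300 mg/g at a single visit into the Aim 2B formula and conclude that power collapses. The endpoint is time to first crossing, so that is the wrong event count.
- A reader might infer that the trial needs more patients. The hypothesised effect stays powered over a wide SD range.

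**Conclusion.** The stated 80% power for 0.24 log units is correct arithmetic on an unsupported input. If the plan's rates describe status at two years, the marginal follow-up SD is at least 0.79 pooled, and unadjusted power for 0.24 is about 0.51 at best (0.31 at SD 1.0). If the rates are cumulative, a marginal SD of 0.58 still has no support; the simulated range is 0.7 to 1.4 under assumed noise and drift. Adjustment and repeated measures may recover some or all of the loss, so the description of the calculation as conservative is unsupported rather than disproved. Power for the hypothesised 0.61 stays at about 80% or more up to an SD of about 1.5.

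The Aim 2B power of more than 95% rests on a 60% SOC event rate that the 10% average rise in the Aim 2C hypothesis does not support. The simulated cumulative rates of 15% to 49% depend on assumed inputs. This is a weakness in the justification of two primary endpoints, not evidence that the design fails.

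**What to change.** In Section 8.0 and Table S1:
- State the Aim 2C detectable effect as 0.41 SD of baseline-adjusted follow-up log uACR.
- Translate it to log units, and show power for both 0.24 and 0.61, over a range of residual SDs (for example 0.4 to 1.5). The paired Aim 1 first-morning samples can inform visit-to-visit noise; a blinded pooled SD from Aim 2 can inform the spread at follow-up.
- Drop or qualify the statement that the calculations are probably conservative.
- Replace the 60% progression and 10% average rise for the SOC arm with a compatible pair. Say whether the progression and regression rates are status at two years or cumulative first crossings, and restate the Aim 2B power from cumulative first-crossing rates.

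The cost is rewording and a small table. Some stated figures may become less favourable. No patients are added.
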